10.4 WCTU responsibilities

Following the initial report, all SAEs should be followed up to resolution wherever possible and further information may be requested by the WCTU. The participant will be identified only by trial number, date of birth and initials. The participant's name should not be used on any correspondence.

Once an SAE is received at the WCTU, it will be evaluated by staff at the WCTU and the CI (or their delegate) for seriousness, expectedness and causality.

The causality assessment given by the PI cannot be overruled by the CI (or their delegate) and in the case of disagreement both opinions will be provided with the report.

ClinicalTrials.gov.: NCT01972451 Page **28** of **42**

The WCTU will report any SUSAEs to the main REC within 15 days of the date the SAE was transmitted to the WCTU.

The WCTU will report a list of all SAEs (expected and unexpected) and any other safety recommendations to the REC, every 12 months, throughout the course of the trial.

ClinicalTrials.gov.: NCT01972451 Page **29** of **42**

11.0 Trial management

11.1 Trial committees and trial management

The conduct of the trial is being overseen by the following committees:

- The Trial Management Group (TMG) will be responsible for the day-to-day running of the trial and will meet initially every month in order to closely manage the study. The TMG members will include the Chief Investigator, other active trial investigators, WCTU representatives, and specialist advisors.
- An independent Trial Steering Committee (TSC) which is a committee of independent members that provides overall supervision of the trial. The role of the TSC is to act on behalf of the sponsor and funder, to provide overall supervision for the trial, to ensure that it is conducted in accordance with GCP, and to provide advice through its independent Chairman. The TSC will decide on continuing or stopping the trial, or modifying the Protocol. It will meet at least annually and will consider the results of other trials and new information which has arisen, and recommend appropriate action.

11.2 Monitoring

The clinical trial risk assessment has been used to determine the intensity and focus of central and onsite monitoring activity in the CONSCOP trial. Low monitoring levels will be employed and are fully documented in the trial monitoring plan.

Investigators must agree to allow trial related monitoring, including audits and regulatory inspections, by providing direct access to source data/documents as required. Patient consent for this will be obtained.

11.3 Participant Withdrawal

In consenting to the trial, participants are consenting to trial investigations, trial follow-up and data collection. Participants may withdraw from the trial at any time.

CONSCOP Withdrawal CRF [contact]

Patients may:

Level 1: Withdraw from the translational study – participants continue follow-up but do not provide translational samples

ClinicalTrials.gov.: NCT01972451 Page **30** of **42**

Level 2: Completely withdraw from the trial – participants stop follow-up and any translational sample collection.

Withdrawal for any reason requires a completed CONSCOP Withdrawal CRF to be faxed to the WCTU with the hard copy to follow soon after. Participants do not have to give a reason for their withdrawal but sites should make a reasonable attempt to find out why.

Data and samples collected prior to participant withdrawal at either of the two levels indicated above will be collected and used for trial analysis by the WCTU.

Patients who withdraw consent prior to the colonoscopy will be treated as having not given consent.

11.4 Protocol/GCP non-compliance

The Principal Investigator should report any non-compliance to the trial protocol or the conditions and principles of Good Clinical Practice to the WCTU as soon as they become aware of it.

11.5 The End of the Trial

The end of the trial is defined as the date of final data capture to meet the trial endpoints. In this case end of trial is defined as when the last patient has undergone their colonoscopy and had associated data collected.

11.6 Archiving

The Trial Master File (TMF) and Investigator Site File (ISF) containing essential documents will be archived at an approved external storage facility for a minimum of 15 years. The WCTU will archive the TMF and TSFs on behalf of the Sponsor. The Principal Investigator is responsible for archival of the ISF at site. Essential documents pertaining to the trial shall not be destroyed without permission from the Sponsor.

ClinicalTrials.gov.: NCT01972451 Page **31** of **42**

12.0 Statistical considerations

12.1 Randomisation

Randomisation will take place centrally at the WCTU using either an automated telephone or a secure online service (see section 7.0). Participants will be randomised using simple randomisation. Randomisation will have an allocation ratio of 1:1.

12.2 Outcome measures, sample size calculations and analyses

This is a feasibility study with the following objectives:

- 1. To assess whether enough participants can be recruited into the study (uptake by both participants and screeners) to suggest that it is feasible to run a future, larger scale trial investigating the impact of enhanced colonoscopy on polyp detection and rate of interval cancer detection on follow up.
- 2. To assess whether the enhanced colonoscopy takes an acceptable length of additional time to conduct
- 3. To estimate the proximal serrated polyp detection rate in the intervention arm to inform the sample size calculation of a future trial by allowing an assessment of the possible magnitude of improvement in cancer detection
- 4. To estimate the proportion of samples that are able to be collected as per protocol to inform the design of the translational element of the future trial
- 5. To assess the feasibility of incorporating an economic evaluation into a larger scale trial by exploring issues relating to collection of data on resource utilization, costs and outcome measures.

The following outcome measures will be used for each objective:

Objective 1: Based on current numbers of participants in the Bowel Cancer Screening Programme, if we were to open the study to recruitment in all centres involved in the Welsh colorectal screening programme for 1 year, we estimate that approximately 2200 patients would attend for colonoscopy following an abnormal faecal occult blood test (FOBT) and would be eligible for inclusion in the study. From experience in other trials in this area, we estimate that the proportion of eligible patients who give consent may be as high as 60%. With 2200 patients, we would be able to estimate this parameter with 95% confidence intervals of ±2%. If recruitment is below 50% then the external validity of the results would be in serious doubt and so we would not proceed to the full study.

Objective 2: will be assessed using a non-inferiority design. Current data from Bowel Screening Wales suggests that the procedure time in the standard colonoscopy control arm has a mean of 30 minutes (SD 15 minutes, normally distributed). Experience suggests that the intervention arm may take 12 minutes longer but should be no more than 15 minutes longer. This will require 1052 patients (power 90%, alpha=0.05 (one sided)) based on a two group t test.

Objective 3: If 60% of all patients were recruited (2200*0.6=1320) then we would be able to estimate the proximal serrated polyp detection rate in the intervention arm (which is estimated to possibly be as high as 9%) with 95% confidence intervals of $\pm 2.2\%$.

Objective 4: If 60% of all patients were recruited (2200*0.6=1320) then we would be able to estimate the proportion of samples that are able to be collected as per protocol (which we would want to be higher than 50%) with 95% confidence intervals of $\pm 2.7\%$.

ClinicalTrials.gov.: NCT01972451 Page **32** of **42**

Objective 5: A preliminary cost-effectiveness analysis will be undertaken alongside the feasibility study to assess whether detailed cost data can be generated and information relating to resource utilisation. Resource utilisation and differences in cost will be studied between the two groups with regard to staff time, consumables used during the procedures, use of sedation and other agents to improve patient comfort. We will however look to using this data input as the basis for a formal cost effectiveness analysis which would be best undertaken as a further study in correlation with the outcomes. A series of sensitivity analyses will be undertaken to determine the extent to which baseline findings are sensitive to parameter variation will inform numbers required to cost-effectiveness analysis within full scale trial.

Criteria for proceeding to a full trial: If objective 1 is passed then objective 2 will be assessed. If objective 2 is passed then results from objective 1 and 3 will be assessed to decide whether or not a full trial assessing impact on cancer rates is achievable in a reasonable time frame.

ClinicalTrials.gov.: NCT01972451 Page **33** of **42**

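### Objective 2: 1052 patients does not follow from one-sided alpha 0.05 and 90% power; it is the figure for one-sided 0.025

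*Protocol*

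**What the plan says.** All the inputs are in Protocol section 12.2 under Objective 2, apart from the allocation ratio.

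- Design: "Objective 2: will be assessed using a non-inferiority design".
- Control-arm procedure time: it "has a mean of 30 minutes (SD 15 minutes, normally distributed").
- Expected excess and limit: "Experience suggests that the intervention arm may take 12 minutes longer but should be no more than 15 minutes longer".
- Result: "This will require 1052 patients (power 90%, alpha=0.05 (one sided)) based on a two group t test".
- Allocation: section 12.1 gives simple randomisation at 1:1.

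No allowance for dropout or missing times is attached to the 1052. The overall target of 1320 participants, 660 per group (sections 2.0 and 2.1), is derived separately in section 12.2 as 60% of about 2200 eligible patients.

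The criteria for proceeding to a full trial, at the end of section 12.2, make Objective 2 a gate. It is assessed only if Objective 1 is passed, and the later decision on feasibility of a full trial is reached only if Objective 2 is passed.

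**The concern.** The sentence fixes alpha, sidedness, power, test and N together, and the other inputs are stated just before it, so the figure can be checked directly. It does not come out. The stated N fits a two-sided 0.05 calculation (one-sided 0.025) that has been labelled one-sided 0.05.

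The consequence is an ambiguous test level for a go/no-go decision. Read literally, the 15-minute limit is compared with the upper end of a two-sided 90% confidence interval. Read through the sample size, it is compared with the upper end of a two-sided 95% interval. If the true excess were exactly 15 minutes, the chance of wrongly declaring it acceptable is 5% on the first reading and 2.5% on the second. The stated power is also not the power of 1052 patients at the stated alpha.

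**Working it through.** **Inputs** (section 12.2, Objective 2, unless noted)

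- SD σ = 15 minutes. It is given for the control arm and assumed here for both arms.
- Expected excess 12 minutes and limit 15 minutes, so the distance to the limit is δ = 15 − 12 = 3 minutes, and δ/σ = 0.2.
- Power 90%: z = 1.2816.
- One-sided alpha 0.05: z = 1.6449. One-sided alpha 0.025: z = 1.9600.
- Allocation 1:1 (section 12.1).

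**Formula** (normal approximation)

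n per arm = 2 (σ/δ)² (z_α + z_power)² = 50 (z_α + z_power)²

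**Reproducing the plan's figure**

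At one-sided 0.025: 50 × (1.9600 + 1.2816)² = 525.4, rounded up to 526 per arm, **1052 in total**. This is the protocol's number. An exact noncentral-t calculation rounds up to 527 per arm (1054).

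**What the stated alpha gives**

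At one-sided 0.05: 50 × (1.6449 + 1.2816)² = 428.2, rounded up to 429 per arm, **858 in total**. The exact t calculation also gives 429 per arm. The gap is 1052 − 858 = 194 patients, and 194/858 is about 23%.

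**Power of the stated and planned numbers** (exact t, difference 3, SD 15)

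| Patients per arm (total) | One-sided 0.05 | One-sided 0.025 |
|---|---|---|
| 526 (1052) | 94.5% | 90.0% (89.98%) |
| 660 (1320) | 97.7% | 95.3% |

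Working backwards by the normal approximation, 526 per arm gives δ / (σ√(2/526)) = 3.2435. Subtracting 1.2816 leaves 1.9619, a one-sided alpha of 0.0249.

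**Other routes to about 1052 at one-sided 0.05**

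- 95% power instead of 90%: 1084.
- 2:1 allocation: 966.
- Inflation for about 20% loss: 858/0.8 = 1073, or 858 × 1.2 = 1030. These are near 1052, but the protocol states no such allowance.
- A larger SD: about 16.6 minutes would be needed, but the protocol states 15.

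None of these both reproduces 1052 and rests on stated inputs.

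**Effect on the gate at 1320 patients**

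SE of the mean difference = 15 × √(2/660) = 0.83 minutes (0.8257 unrounded). The test passes if the observed excess is below:

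- 15 − 1.645 × 0.8257 = **13.64 minutes** at one-sided 0.05;
- 15 − 1.960 × 0.8257 = **13.38 minutes** at one-sided 0.025.

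The two readings disagree over a band of 0.26 minutes. The chance of landing in it is about 2.4% if the true excess is 12 minutes, and about 12.5% if it is 13.5 minutes.

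**The case against.** The arithmetic is hard to dispute; the case on the other side is about how much it matters.

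- **The error is on the safe side for power.** This stands. 1052 is more than the stated alpha needs. Objective 2 is reached only if recruitment is at least 50% of about 2200, which is about 1100 patients if that estimate holds. That exceeds 1052, so power is at least 90% at either level. The 1320 target does not depend on the 1052.
- **Testing at one-sided 0.05 does not inflate the error rate above the level the protocol states.** This also stands. The comparison of 5% with 2.5% is with a level inferred from N, which the protocol nowhere writes down. One-sided 0.05 could be a deliberate choice for a feasibility gate, so either alpha or N may be the slip.
- **The match at 0.025 is not perfect.** By strict exact-t rounding the figure is 1054, not 1052. A difference of 2 patients does not compete with a gap of 194.
- **The practical band is narrow**, at 0.26 minutes. That is true, and it limits the harm. It does not settle which threshold applies.
- **A SAP may set the confidence-interval rule.** It may, but it cannot make the sentence in section 12.2 correct, because that sentence itself fixes alpha, power and N.

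**Conclusion.** The point holds. With the protocol's own inputs, 1052 patients, 90% power and one-sided alpha 0.05 are incompatible. One-sided 0.05 needs 858 patients, and 1052 patients at that level have 94.5% power. The likeliest explanation is a calculation at two-sided 0.05 (one-sided 0.025) reported as one-sided 0.05, though the document cannot show which figure was intended.

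The conclusion assumes a common SD of 15 minutes, equal arms and no hidden allowance for loss, all consistent with what section 12.2 and section 12.1 state. It is not a shortage of patients. It is a misreported design and an undefined test level for a go/no-go gate, with pass thresholds of 13.64 or 13.38 minutes at the planned 1320.

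**What to change.** The sponsor should confirm the intended one-sided level and correct the Objective 2 sentence in section 12.2 in one of two ways:

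1. State alpha as 0.025 (one-sided), keep 1052 patients and 90% power, and say that the upper limit of the two-sided 95% confidence interval for the mean difference must lie below 15 minutes.
2. Keep alpha at 0.05 (one-sided) and restate the requirement as 858 patients, or state the power as 94.5% at 1052. The corresponding rule uses the upper limit of the two-sided 90% interval.

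The chosen level should be repeated in the criteria for proceeding to a full trial at the end of section 12.2, and settled before procedure times are compared between arms. If an allowance for loss or a larger SD lies behind the 1052, it should be stated.

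The cost is one corrected sentence and a matching line in the decision rule. No extra patients are needed, since 1320 give 95.3% power at one-sided 0.025 and 97.7% at one-sided 0.05.

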2.1 Lay summary

Colorectal cancer is the second leading cause of cancer deaths in the UK (1). The Bowel Cancer Screening Programme (BCSP) was implemented to reduce deaths by the early prevention and detection of bowel cancer. Results from the first few years of screening and previous smaller studies show that while in its current form it will save many lives, there continue to be polyps and cancers in the right side of the colon that may be difficult to detect. There is some evidence that these types of polyps (serrated polyps) may be at least partly responsible for cancers missed at the initial colonoscopy and have a faster rate of growth to cancer compared to conventional polyps (adenomas).

We propose to examine participants undergoing screening colonoscopy with the addition of a contrast dye (a safe food colouring agent base already used in various bowel camera procedures in standard clinical practice). This has been shown to improve detection of conventional polyps significantly (2) and only takes a few more minutes of extra time. The study is a randomised controlled feasibility study comparing two groups, with and without use of dye spray throughout the right colon. Our primary aim is to study the feasibility of undertaking these procedures (i.e. assessment of acceptability by participants and colonoscopists, including time and costs involved in undertaking the enhanced approach). In addition to this we will also be assessing whether this technique helps to improve the detection rates of right-sided polyps in order to inform the sample size for a larger study. Removal of these polyps will enable further laboratory analysis of a collection of polyp samples in order to assess if such a sample collection might be able to answer the question of biological behaviour and growth pattern to cancer in a larger subsequent study within the BCSP. This will help to inform further studies to assess the impact of improved detection and potentially reduced incidence of interval or missed bowel cancers in longer term follow up.

We aim to recruit 1320 participants (660 per group) over a 12-month period involving all participating bowel cancer screening centres in Wales. All eligible participants (eligibility confirmed by SSP) undertaking the BCSP will be invited to the study and participant randomisation will be performed centrally. The data collected by the BCSP nurse will include all the performance parameters already undertaken as part of the BCSP.

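### Objective 3 is set on the intervention arm alone, so as written it cannot show the improvement in detection it is meant to inform, although both randomised arms are measured

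*Protocol*

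**What the plan says.** Objective 3 appears in the synopsis (section 2.0), in section 3.0 (Specific Objectives) and in section 12.2. Each time the quantity to be estimated is the detection rate in the intervention arm. Section 12.2 gives the reason: "to inform the sample size calculation of a future trial by allowing an assessment of the possible magnitude of improvement in cancer detection". The precision statement there is also for one arm: "we would be able to estimate the proximal serrated polyp detection rate in the intervention arm", a rate "which is estimated to possibly be as high as 9" per cent, with a 95% confidence interval of ±2.2%.

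The criteria for proceeding, at the end of section 12.2, use this objective once Objectives 1 and 2 are passed: "results from objective 1 and 3 will be assessed to decide whether or not a full trial assessing impact on cancer rates is achievable".

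Other parts of the protocol are wider. The endpoint list in the synopsis gives the proximal serrated polyp detection rate without restricting it to an arm. The lay summary (section 2.1) states a comparative intention: "we will also be assessing whether this technique helps to improve the detection rates of right-sided polyps". Section 9.1 has polyp number, location and histology recorded for consenting participants in general, and section 9.2 sends polyps at or above the splenic flexure from all trial participants to central review.

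**The concern.** Improvement is a difference between two rates, and Objective 3 names one. No control-arm rate, expected difference or external reference rate for proximal serrated polyps is given anywhere in the protocol. A dye-arm rate of 9% is what one would see with a control rate of 3% and a large gain, or with a control rate of 9% and no gain. The estimate alone does not separate these.

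A published rate is not a secure stand-in by the protocol's own account: section 3.0 describes the evidence on right-sided serrated polyps as small, retrospective and widely varying. Objective 2, by contrast, states a control mean and SD, and Objective 5 refers to differences between the two groups.

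At stake is whether Objective 3 can serve its stated purpose, and whether those deciding on a full trial have the randomised comparison in front of them.

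**Working it through.** **Inputs from the protocol.** Intervention-arm rate 9% (section 12.2). Eligible patients 2200 and consent 60%, hence 1320 recruited (section 12.2). 660 per group (section 2.1: "We aim to recruit 1320 participants (660 per group) over a 12-month period"). Allocation 1:1 (section 12.1). Consent below 50% means not proceeding (section 12.2, Objective 1).

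**Assumption.** The control rate p0 is not in the protocol. It is taken over a range from 3% to 9%.

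**Step 1: reproduce the plan's figure.** Half-width for one proportion = 1.96 × √[p(1−p)/n], with p = 0.09 and p(1−p) = 0.0819.
- n = 660: 1.96 × √(0.0819/660) = 0.0218, or ±2.2 points. This matches.
- n = 1320: 1.96 × √(0.0819/1320) = 0.0154, or ±1.5 points. This does not match.

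The stated precision is correct, and it is a one-arm figure.

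**Step 2: precision of the difference at 60% consent (660 per arm).** Half-width = 1.96 × √[(0.0819 + p0(1−p0))/660].

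| Assumed p0 | Difference (points) | Half-width (points) | 95% CI (points) |
|---|---|---|---|
| 3% | 6.0 | ±2.5 | 3.5 to 8.5 |
| 5% | 4.0 | ±2.7 | 1.3 to 6.7 |
| 7% | 2.0 | ±2.9 | −0.9 to 4.9 |
| 9% | 0.0 | ±3.1 | −3.1 to 3.1 |

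**Step 3: the same at 50% consent.** 2200 × 0.5 = 1100, or 550 per arm.
- p0 = 3%: 1.96 × √[(0.0819 + 0.0291)/550] = 0.0278, or ±2.8 points.
- p0 = 9%: 1.96 × √[(0.0819 + 0.0819)/550] = 0.0338, or ±3.4 points.

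**Reading.** The planned patients give a usable estimate of the difference. A gain of about 2 points or less would have an interval that includes zero, which is why the comparison belongs in the plan as estimation.

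**The case against.** The strongest reply is that the comparison is already implied. The endpoint is listed without an arm, both arms are measured, the lay summary speaks of improvement, and the way an endpoint is tabulated by arm is commonly left to the SAP, which is not at hand. That stands as far as the data go: a reader might infer that the trial cannot show improvement, and the protocol does not support that. The limit lies in Objective 3 as worded. It is more than a missing analysis line, because the protocol itself fixes the target and its precision on one arm.

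Four further inferences go too far:
- **That the proceed criteria treat a 9% versus 9% result like 9% versus 3%.** Section 12.2 sets no threshold or mechanical rule for Objective 3. It says only that the results will be assessed.
- **That the lay summary flatly contradicts Objective 3.** It speaks of right-sided polyps in general, while Objective 3 concerns serrated ones. The objective is narrower than the aim, which is a looser mismatch.
- **That progression should depend on the confidence interval of the difference.** That would add a debatable efficacy gate to a study whose primary aim is feasibility.
- **That a polyp-rate difference would settle the next sample size.** The stated target is improvement in cancer detection, and section 4.0 describes a future trial powered for bowel cancer mortality. A sample size worked out for a polyp-detection comparison would not be the size of that trial.

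**Conclusion.** The point holds in a limited form. Objective 3 and its precision statement target the intervention arm only, while the purpose is an assessment of improvement. With no control rate in the protocol, the one-arm estimate alone cannot provide that. The ±2.2% is arithmetically right but describes a quantity that does not answer the question.

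The randomised difference is available from the planned participants. Its precision is about ±2.5 to ±3.1 points at 660 per arm, or ±2.8 to ±3.4 at 550 per arm. These figures rest on a dye-arm rate of 9%, assumed control rates of 3% to 9%, equal arms, and consent of 60% or 50% of 2200. The protocol itself calls the 9% and the 60% possible upper values. The change is worth making, but its absence does not undermine the trial's data or its feasibility aims.

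**What to change.** - **Objective 3 (synopsis, section 3.0, section 12.2):** reword it to estimate the proximal serrated polyp detection rate in each arm and the between-arm difference with a 95% CI. State that this is estimation and not a hypothesis test.
- **Precision statement (section 12.2):** keep the ±2.2% for the dye arm and add the precision of the difference as a conditional range, naming the assumed control rates and the consent level.
- **Criteria for proceeding (section 12.2):** say that the assessment of Objective 3 will consider the between-arm difference, with no pass/fail rule based on its interval.
- **Interpretation:** note that a polyp-rate difference is a surrogate, and that sizing the full trial needs a further link from polyp detection to cancer outcomes.

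The cost is wording in three sections. No extra patients or data items are needed, because sections 9.1 and 9.2 already cover both arms.

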- 3. Anyone with a known allergy to a food colouring agent.
- 4. Previous inclusion in the trial

See Section 6.2 for full exclusion criteria.

Interventions:

Arm A: Colonoscopy without enhanced dye

Arm B: Colonoscopy with enhanced dye

Trial assessments:

At colonoscopy data will be collected on the procedure logistics (time, completion, resource utilisation), associated adverse events, results and patient comfort (see section 9).

Additionally, after local reporting, all proximal colonic polyps (i.e. above the splenic flexure) should be sent for central analysis (see section 13)

Endpoints:

- Proportion of screening service providers who agree to participate in the trial
- Proportion of eligible patients who give consent.
- Procedure time
- Colonoscopy completion rate
- Proximal serrated polyps detection rate
- Proportion of proximal polyp samples that are able to be collected as per protocol
- Resource utilisation: staff time, consumables used during the procedures, use of sedation and other agents to improve patient comfort.
- Adverse events
- Patient comfort scores

ClinicalTrials.gov.: NCT01972451 Page **13** of **42**

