9.2 Central review of polyps found at the splenic flexure or above

After local reporting, all polyps found at the splenic flexure or above in all trial participants should be sent for central review (see section 13). Using data uploaded to BSIMS (see 9.1 above), the central study team will work out which patients had right sided polyps and will request these directly from the appropriate local pathology department. The local pathology department will send the requested paraffin blocks to the pathology laboratory in Cardiff following the instructions in the letter.

9.3 Follow up in routine datasets of all patients up to 30 days after colonoscopy

Public Health Wales will obtain the following data from routine datasets for each participant:

7 day and 30 day hospital re-admission rates (late complications)

Public Health Wales will provide this BSIMS data to WCTU for analysis.

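### The ±2.7% precision for Objective 4 counts every one of the 1320 participants as a sample, although only those with a proximal polyp can supply one

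*Protocol*

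**What the plan says.** Protocol section 12.2 introduces the Objective 4 calculation with "If 60% of all patients were recruited (2200*0.6=1320") and says that on this basis "we would be able to estimate the proportion of samples that are able to be collected as per protocol". The proportion is described as one "which we would want to be higher than 50" per cent, and the 95% interval is given as ±2.7%.

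The endpoint list in section 2.0 words the quantity as "Proportion of proximal polyp samples that are able to be collected as per protocol".

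Section 9.2 says which tissue this covers: "all polyps found at the splenic flexure or above in all trial participants should be sent for central review". It also describes the route: from the data uploaded to the screening information system, "the central study team will work out which patients had right sided polyps and will request these directly" from the local pathology department. Section 13.0 repeats that route.

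The protocol gives no expected number of proximal polyps and no expected share of participants with one. The only related rate is in Objective 3 of section 12.2: the proximal serrated polyp detection rate in the intervention arm, "which is estimated to possibly be as high as 9" per cent.

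**The concern.** A participant with no polyp at or above the splenic flexure has nothing to send, so cannot count as a success or a failure for this endpoint. The denominator must be proximal polyps, or participants who have at least one. The precision statement uses everyone recruited.

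Objective 4 is meant to inform the design of the translational part of a later trial, and the protocol attaches a 50% benchmark to it. A planner who takes ±2.7 points at face value would expect, for example, an observed 53% to lie clear of 50%. With fewer contributors it may not: at ±3.8 points the interval around 53% is about 49% to 57%.

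**Working it through.** **Inputs**

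- Recruited participants: 2200 × 0.6 = 1320, both arms together (section 12.2).
- Proportion: 0.50, the stated benchmark and also the value that gives the widest interval.
- Confidence: 95% two-sided, multiplier 1.96.
- Share of participants with any proximal polyp: not given. A range of 20% to 60% is assumed below.
- Polyps per contributing patient and their within-patient correlation: not given. Illustrative values are used.

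**Step 1. Reproduce the stated figure.** Half-width = 1.96 × √(p(1−p)/n).

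- p = 0.50, n = 1320: 1.96 × √(0.25/1320) = 2.70%, which matches.
- p = 0.50, n = 660 (one arm): 3.81%, no match.
- n = 1320 with p = 0.60 or 0.70: 2.64% or 2.47%, no match.
- At p = 0.50, only n between about 1270 and 1368 rounds to 2.7%.

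The denominator was therefore all 1320 participants.

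**Step 2. Compare the neighbouring objective.** Objective 3 opens with the same 1320 but concerns the intervention arm only. Its ±2.2% is 1.96 × √(0.09 × 0.91/660) = 2.18%; with n = 1320 it would be 1.54%. That calculation was restricted to the relevant group, and the one for Objective 4 was not.

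**Step 3. Unit = participant with at least one proximal polyp, p = 0.50.**

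| Assumed share with a proximal polyp | Contributing participants | Half-width (points) | Ratio to 2.70 |
|---|---|---|---|
| 20% | 264 | ±6.0 | 2.2 |
| 30% | 396 | ±4.9 | 1.8 |
| 40% | 528 | ±4.3 | 1.6 |
| 50% | 660 | ±3.8 | 1.4 |
| 60% | 792 | ±3.5 | 1.3 |

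**Step 4. Unit = polyp.** With m polyps per contributing patient and intraclass correlation ICC, the variance is multiplied by 1 + (m − 1) × ICC. At p = 0.50:

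- 50% of participants with two polyps each: 660 × 2 = 1320 polyps. ICC 0 gives ±2.7. ICC 0.5 gives 2.70 × √1.5 = ±3.3.
- 30% of participants with two polyps each: 396 × 2 = 792 polyps. ICC 0 gives ±3.5. ICC 0.5 gives 3.48 × √1.5 = ±4.3.
- 50% of participants with 2.5 polyps each: 660 × 2.5 = 1650 polyps. ICC 0 gives ±2.4. ICC 0.5 gives 2.41 × √1.75 = ±3.2.

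**Step 5. Serrated polyps only, as a subset.** If the 9% upper figure for the intervention arm also held in the control arm (assumption), 0.09 × 1320 is about 119 participants, and 1.96 × √(0.25/119) = ±9.0 points.

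**The case against.** Four points can be made for the protocol.

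- **The endpoint counts samples, and one patient may supply several.** This stands in part. Enough polyps per patient could bring the half-width to ±2.7 or slightly below, as Step 4 shows. That needs both a high polyp count and little within-patient correlation, and the protocol states neither. Agreement with 1320 would be a coincidence.
- **The proportion may be well above 50%, which narrows the interval.** This is true: at p = 0.80, n = 660 gives ±3.1, and at p = 0.90 about 474 contributors give ±2.7. But the stated figure was itself computed at 50%, so this does not support the denominator used.
- **A planning half-width does not decide how the result is read.** This stands. The reported interval will come from the samples actually observed, and nothing in the protocol says ±2.7% will be attached to the result.
- **Nothing decisive depends on Objective 4.** This also stands. The criteria in section 12.2 for proceeding to a full trial use Objectives 1, 2 and 3. The 50% is a stated wish with no test attached. The 1320 comes from expected recruitment, so correcting this figure changes no sample size.

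A reader might go further and infer that the precision is wrong several times over, by applying the 9% serrated rate and arriving at ±9.0 points or worse. The documents do not support that as the size of the error. Section 9.2 sends all polyps at or above the splenic flexure, from all participants, so the collection endpoint is restricted neither by histology nor by arm. Serrated polyps are the target of the genetic work in section 13.0, and they form a subset of what is collected.

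How a clustered interval would be computed is commonly left to an analysis plan, and its absence here is no part of the error.

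**Conclusion.** The point holds in a limited form. It is certain that ±2.7% rests on all 1320 participants, and that the protocol's own endpoint and collection route exclude those without a proximal polyp. The stated precision is therefore unsupported.

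That it is too narrow is probable, but the size is not established. Per contributing participant, it is about 1.3 to 2.2 times too narrow if 20% to 60% of participants have a proximal polyp, a range that is assumed. Per polyp, the shortfall could be smaller or could vanish, depending on a polyp count and a correlation that the protocol does not give. To call the interval far too narrow would go beyond the documents.

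The severity is moderate. A stated figure is wrong on its own terms and feeds the planning of the translational work, but no progression criterion or sample size depends on it.

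**What to change.** In Protocol section 12.2, Objective 4:

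1. Define the denominator as participants with at least one proximal polyp, or as proximal polyps with an interval that allows for clustering within patients.
2. State the expected number of such participants or polyps and its source.
3. Replace ±2.7% with the half-width for that number. If the rate is uncertain, give a short table at a proportion of 50%: 264 contributors ±6.0, 396 ±4.9, 660 ±3.8 points.
4. If the serrated case is of interest, show it only as a labelled subset: about 119 participants, ±9.0 points, assuming the 9% rate in both arms.

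The cost is a sentence or a small table. The stated precision will look less favourable. No extra patients are needed and the progression criteria do not change.
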